PROTOCOL of the study

Versie 1 – 21 december 2023

Integrated genetic and functional analysis of the influence of menstrual products on intimate female health (abbreviated as 'Luna' project).

Research study at Antwerp University Hospital and the University of Antwerp, in a collaboration between Faculty of Medicine and Health Sciences and Faculty of Science, Department of Bioengineering

Inclusion/exclusion criteria

Volunteers
Age: 18+
Gender: F
Not pregnant
Not menopausal
Natural menstrual cycle, copper IUD or combination pill
Regular menstrual cycle
No reproductive disease (endometriosis, PCOS,..)
No history of Toxic Shock Syndrome (TSS), sensitivity or allergy to menstrual hygiene products

Furthermore, selections will be made based on the questionnaire in order to achieve a balanced study population.

Recruitment of participants

The volunteers (n=500) will be recruited through the channels built up in the Isala project (EDGE000471), such as the website (www.isala.be), instagram (Isala_UAntwerp), twitter (Isala_UAntwerp) and Linkedin (Isala). Thus, a large community has already been built, consisting of women who are very eager to participate in follow-up research. These channels will be used to obtain a representative group. Staff and students of the UAntwerpen and the UZA will also be recruited through posters, ad valvas and mails. No students will be recruited who have yet to take exams from the relevant members of the study. The volunteers will receive the information about the study and a consent form during information sessions, during which the self-sampling kit and menstrual products can also be distributed.

[figure not shown]
Sample collection

Samples will be self-sampled by the selected volunteers (n = 100). The self-sampling kit contains a detailed manual, information brochure and all materials needed by the volunteers for sample collection, storage and delivery to [name] lab. Participants will have 3 sample collections for each menstrual product. This will consist of a vaginal, vulvar and groin swab, and during menstruation the menstrual blood will also be collected, this in the case of the cup directly and in the case of the other products as the product itself, this via non-transparent sterile sealed bags provided for this purpose. These products are a tampon, a sanitary pad, a menstrual cup and 2 types of menstrual underwear, 1 with a cotton lining and 1 with a bamboo lining.

TIMELINE LUNA

[figure not shown]
Participants

- n = 100 for 5 menstrual cycles use each cycle another menstrual hygiene product
- n = 50 combination pill, n = 50 natural cycle (no hormonal contraception)
 - Regular (predicable) menstrual cycle
 - No reproductive condition that could affect the menstrual cycle (Endometriosis, endometritis, PCOS)
 - No vaginal irritations in the last 3months
 - No pregnancy desire in the next 5 months
 - No allergies/sensitivity, no history of TSS
 - No antibiotics/antimycotics/probiotics in the last 3 months
 - No probiotics and vaginal douching during the study

Sample type

- Menstrual blood/tampon/pad/underwear
Groin skin swab
Vulvar swab
Vaginal swab

[figure not shown]

Collection procedure

- Menstrual blood collection
- Tampon/Menstrual pad/Menstruation underwear collection

Techniques

- Microbial profiling (Shotgun sequencing)
 - All samples
- Untargeted metabolomics
 - Vaginal swab
 - Menstrual blood (via cup)
- Immunological assay (ELISA)
 - Vaginal swab
 - Menstrual blood (via cup)

Sample size calculation

Power analyses are challenging for microbiome studies because the magnitude and variance of effects on the microbiome are unknown and are highly individual-dependent and different for each bacterium. However, from literature review and our experience with the Isala study, we assume that the sample size selected is reasonable. Thus, initially recruited participants (n=1500) will complete a

comprehensive questionnaire regarding their health, lifestyle, menstrual hygiene and vaginal hygiene. Based on this questionnaire, a selection will be made ($n = 100$) of participants who will participate in the actual intervention study, in order to obtain a balanced study population, as well as based on location to make the study logistically feasible.

Thus, with 50 participants per condition (half natural cycle, half combined pill) in time series, we can perform paired analyses that allow us to account for intra-personal variation and increase power. Due to the nature of the study, no wash-out period will be necessary during the different interventions, as this is already natural between 2 menstruations, this also makes each participant a separate control and does not require varying the order of menstrual products. From our own experience with longitudinal studies, we take into account 5-10% dropout. If it is larger, we will recruit additional participants to avoid undermining the study.

We examine the influence of menstrual products at different levels. A PERMANOVA test will allow us to examine the overall effect of the intervention on the composition of the microbiome. Furthermore, we will investigate the effect on alpha diversity, for which health associations are known in the vaginal microbiome. This can be examined with a mixed effect model. Differential abundance of individual taxa will also be tested. It has been found that test tools for differential abundance often do not agree in reported results. To compensate for this, we have developed a consensus-based way in which several differential abundance testing tools are used and a taxon/condition is considered significant only if multiple tools agree. Three tools are capable of including random effects for paired analysis. Finally, for the vaginal microbiome, we test the effect on taxa modules known to be associated with lifestyle factors. This multi-level approach gives us a broad view to detect effects that may not be visible at a single individual level.

Analysis of samples

Laboratory of Applied Microbiology and Biotechnology [name], Faculty of Science, Department of Bioengineering, UAntwerpen

Part 1: Microbiome Analysis

Microbial DNA and RNA will be isolated from swabs and menstrual blood (collected via menstrual cups and extracted from the other menstrual products) via a commercial extraction kit such as the Qiagen PowerFecal DNA kit and the Qiagen RNeasy kits (cfr. Human Microbiome Project). The isolated DNA and RNA (converted to cDNA) will then be analyzed via shotgun sequencing and (meta)transcriptomics. Shotgun sequencing

and (meta)transcriptomics allow to study the functional profiles and composition of these microbial communities. Combined, these techniques will provide valuable insights into better understanding the role of microbial communities in the context of health and the influence by menstrual products. The Illumina sequencing platform will be used.

Milestone: Identification of the (functional) microbiome composition of swabs and menstrual blood, with the aim of mapping the influence of menstrual products

Part 2: Quantitative analysis of concentration of specific microorganisms

Using quantitative real-time polymerase chain reaction (qPCR), species- or genus-specific primers will be used to estimate the concentration of specific microorganisms. In qPCR, the amount of a specific piece of DNA is measured in “real time. This allows the initial concentration of this specific DNA to be determined. The results then provide a picture of the concentration of different microorganisms in a sample. For processing these data, the “Minimum Information for Publication of Quantitative Real-Time PCR Experiments” (MIQE) guidelines will be used.

Milestone: Absolute abundance of microorganisms in swabs and menstrual blood, with the aim of mapping the influence of menstrual products

Part 3: Identification and quantification of metabolites from swabs or menstrual blood via a cup

In addition to the identification and quantification of specific microorganisms from swabs and menstrual blood, it is also interesting to look at what metabolites are produced by these microorganisms, and whether any toxins or allergens might be found in the fluid/blood. These could be from menstrual products. This can be found out using metabolomics. Specifically, liquid chromatography and mass spectrometry will be applied to supernatant solutions that will be further prepared by extraction with a cold organic solvent after addition of an internal standard mixture. The MassHunter Quantitative/Qualitative Analysis Software will then be used for identification and quantification of metabolites. Finally, the Mass Profiler Professional will be used for peak alignment, allowing metabolite annotation and statistical analysis.

Milestone: Identification and quantification of metabolites from swabs and menstrual blood, with the goal of mapping the influence of menstrual products

Part 4: Cultivating microorganisms from swabs and menstrual blood

Besides studying the composition of the microbiome through DNA sequencing technology, studying a microbiome through culture techniques remains a relevant way. Namely, low abundant members that might be missed by DNA sequencing techniques can be found, as well as individual strains examined in detail. This may be relevant to find differences in niche-specific strains adapted to conditions on the skin, in the vagina and specifically occurring in menstrual blood. Furthermore, this is expected to isolate a large proportion of lactic acid bacteria, which are of interest because they have a GRAS status (“Generally Recognized As Safe”) and numerous health effects have been extensively described. Consequently, we will plate swabs and menstrual blood from the volunteers on both selective media for lactic acid bacteria, e.g. MRS (de Man Rogosa and Sharpe) medium and blood agar, and rich general media for other bacteria and fungi such as nutrient agar and yeast extract peptone medium (YPD). For this purpose, swabs or menstrual blood will be dissolved in PBS (Phosphate Buffered Saline) and after thorough mixing, a dilution series will be plated out. Several colonies will be highlighted and further identification at species level will be done via colony PCR with universal primers for the 16S rRNA gene (e.g. 8F-1525R) for bacteria and ITS primers for fungi, followed by Sanger sequencing and alignment against a reference genome (e.g. BLAST and EZBioCloud).

Milestone: Cultivation of niche-specific microorganisms.

Part 5: Identification of pro-inflammatory cytokines in swabs and menstrual blood

Besides changes in the microbiome composition due to menstrual products, it is also important to look at possible effects on the immune system of the participants. To investigate this, various immunoassays will be performed on the samples, including ELISAs for antibodies and pro-inflammatory cytokines, chemokines and growth factors (e.g. osteopontin, TGF- β superfamily, VEGF, CXCL10, CCL3, GM-CSF, IL-1 β , IL-2, IL-6, IL-8, IL-12, IL-15, IL-18, XCL1, TNF, IFN- γ , perforin and granzyme etc.) In addition, relevant immune cell populations (e.g. neutrophils, T-cells, ...) and cell-surface receptors will be quantified using flow cytometry.

Milestone: Identification of differentially expressed immune factors, such as cytokines, antibodies and surface molecules.

Part 6: isolation of MAIT cells

A unique goal in this study is the isolation and quantification of white blood cells in menstrual blood, also called “menstrual blood mononuclear cells” or MBMCs. To this end, the blood samples (obtained using the vaginal cup) are processed in analogy to standard blood samples (separation based on a density gradient (e.g. Sepmate tube)

and freezing). The MBMCs are used purely for the quantification of immune responses after co-incubation with microbial (vaginal) isolates: the quantification of cell-surface receptors (via e.g. flow cytometry, ELISA, fluorescence microscopy), cytokines/chemokines and gene expression. In no case will the material be used for elaboration of cell lines.

Milestone: Isolation of MBMCs with enrichment of MAIT cell subpopulation for studying immune responses (cell surface receptors, cytokine production, gene expression of immune signaling).

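### Antibiotics and antimycotics are barred for 3 months before entry but missing from the on-study rule; under a single product order, recently treated samples would fall more on later products than on the first

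*Protocol*

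**What the plan says.** The Participants list sets an entry rule, "No antibiotics/antimycotics/probiotics in the last 3 months", and directly after it the only rule for conduct during the study, "No probiotics and vaginal douching during the study". Probiotics appear in both lines; antibiotics and antimycotics appear only in the first.

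The same list describes the schedule as "n = 100 for 5 menstrual cycles use each cycle another menstrual hygiene product", and the pregnancy criterion, "No pregnancy desire in the next 5 months", implies a horizon of about 5 months.

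The Sample size calculation section states that "no wash-out period will be necessary during the different interventions, as this is already natural between 2 menstruations" and that the design "does not require varying the order of menstrual products". It relies on pairing: "we can perform paired analyses that allow us to account for intra-personal variation and increase power". The paragraph that follows names the tests. For composition, "A PERMANOVA test will allow us to examine the overall effect of the intervention on the composition of the microbiome"; alpha diversity goes into a mixed effect model, and individual taxa are tested for differential abundance.

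The readable text describes no record of an antibiotic or antimycotic course taken during the five cycles and no handling of samples taken after one. The timeline figure is not shown, and the manual in the sampling kit is not at hand.

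**The concern.** By its entry rule the protocol asks for 3 months clear of these drugs before it samples a woman's microbiome. That standard is secured at the start of the first product cycle and at no later point. The interval between two menstruations, which the protocol accepts as wash-out between products, is much shorter than 3 months, so one course can affect the samples of about three later products.

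The consequence is not only added noise. Everyone is clear at entry, and a course can affect only the samples taken after it. If the products come in the same order for all women, recently treated samples are therefore rare under the first product and more common under the later ones. A paired analysis removes what is stable in a woman. It does not remove an exposure that begins partway through her participation. The effect of the course would then be read as an effect of the later product. The same happens when the course treats a reaction to an earlier product: the change is credited to the products that follow.

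**Working it through.** The protocol gives no treatment rate, effect size, standard deviation or error rate, so there is no stated figure to reproduce. The check asks in which direction the gap acts and how large it could be.

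**Inputs from the protocol:** 100 women; 5 cycles, one product each; a 3-month window at entry; 5-10% dropout (95 women are used below).

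**Assumptions:** one cycle is about one month; 1%, 2% or 5% of women start a course per cycle; all women follow one order; total SD 1 and within-woman correlation 0.5; a course shifts alpha diversity by 0.5 or 1 SD, in the same direction for every course.

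**Step 1: share of women inside the window at product position k.** If each course falls after that cycle's collections, the share is 1 - (1 - p)^min(k - 1, 3). If time is counted at mid-cycle, with rate r per woman-month, it is 1 - exp(-r × min(k - 0.5, 3)).

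| Rate | After collections, positions 1-5 | Mid-cycle, positions 1-5 |
|---|---|---|
| 1% | 0 / 1.0 / 2.0 / 3.0 / 3.0% | 0.5 / 1.5 / 2.5 / 3.0 / 3.0% |
| 2% | 0 / 2.0 / 4.0 / 5.9 / 5.9% | 1.0 / 3.0 / 4.9 / 5.8 / 5.8% |
| 5% | 0 / 5.0 / 9.8 / 14.3 / 14.3% | 2.5 / 7.2 / 11.8 / 13.9 / 13.9% |

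Under both timings the share rises to the fourth product and then levels off, because the window spans three cycles. Summed over the five positions, the first timing gives 8.9, 17.7 and 43.3 affected product cycles per 100 women. Out of 500 product cycles that is 1.8%, 3.5% and 8.7%.

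**Step 2: fourth versus first product, analytic.** The bias is the difference in shares times the shift. The SE of the paired difference is sqrt(2 × (1 - 0.5)/95) = 1/sqrt(95) = 0.103 SD. The false-positive rate of a two-sided 5% test is Φ(z - 1.96) + Φ(-z - 1.96), with z = bias/SE. For a constant shift of 1 SD:

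- Rate 1%, after collections: z = 0.0297/0.1026 = 0.29, rate 6.0%.
- Rate 2%, after collections: z = 0.0588/0.1026 = 0.57, rate 8.8%. Mid-cycle: z = 0.0483/0.1026 = 0.47, rate 7.6%.
- Rate 5%, after collections: z = 0.1426/0.1026 = 1.39, rate about 28%. Mid-cycle: z = 0.1146/0.1026 = 1.12, rate about 20%.

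With a shift of 0.5 SD at rate 5%, z halves to 0.70 and the rate is 10.7%; at mid-cycle, z = 0.56 and the rate is 8.6%.

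**Step 3: simulation.** There were 4,000 runs per setting, with 95 women × 5 cycles, no true product effect, courses after that cycle's collections, and a shift of 0.5 or 1 SD over the next three cycles, either constant or fading (1, 2/3, 1/3). The model was a within-woman linear model with product terms. Monte Carlo error is about 0.35 points at 5%. False-positive rates across these settings:

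| Rate | Global product test | Fourth v first |
|---|---|---|
| 1% | 5.1-5.7% | 4.8-6.2% |
| 2% | 5.1-7.5% | 5.6-9.9% |
| 5% | 6.8-21.4% | 7.3-26.2% |

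Leaving out samples inside the window gives 4.5-5.5% in all settings. With a random product order and all data kept, the highest setting (5%, 1 SD, constant) gives 5.4% for the global test and 5.6% for fourth versus first.

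**The case against.** The strongest reply has five parts.

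- **The omission can be defended.** Probiotics and douching are elective and can be barred. Antibiotics and antimycotics are usually taken for a medical reason and cannot be. This stands as far as a ban goes: an extended rule would prevent few courses. It does not answer the need to know when a course was taken.
- **Other documents may cover it.** Excluding samples is a usual matter for a statistical analysis plan, and the kit manual or timeline figure may provide a treatment record. This stands in part. A later exclusion is possible only if the dates were collected, and the on-study rule itself belongs to the protocol and is visibly narrower than the entry rule beside it. A reader might infer that no record will be kept at all; the documents at hand do not show that.
- **The bias belongs to the product order.** It is directional only if all women follow one order. This stands. The protocol says that variation is not required, which is not quite a statement that the order is fixed, and the missing figure could show otherwise. With a varied order, treated samples would still add noise.
- **The large figures need several assumptions at once.** They need a 5% rate (1 - 0.95^4, about 19% of women treated before the fifth product), a full 1 SD shift that does not fade, one direction for every course, and courses placed after that cycle's collections. The documents support none of these. The women are also selected for having had no vaginal irritation and no such treatment for 3 months, and the 3-month window may be a cautious screening margin rather than the length of an effect. All of this stands.
- **The contrast was simplified.** The Sample collection section gives three collections per product, whereas the simulation uses one value per cycle and only alpha diversity. If products are compared on change within a cycle, a shift that is constant across the cycle cancels. The protocol does not settle which contrast is used, so this also stands.

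**Conclusion.** The concern holds in a limited form. The entry and on-study rules do not match, and under a single product order the mismatch acts in one direction: recently treated samples are rarer under the first product and rise to a plateau at the fourth and fifth. The planned pairing does not correct this.

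A reader might infer that the product comparison is therefore invalid, or that its false-positive rate is 20% or more. The documents do not support that. At about 1% of women treated per cycle the effect is negligible (at most about 6%). At 2% it is small (at most 7.5% for the global test and 9.9% for fourth versus first). It becomes material only near 5% with a large and lasting shift. It shrinks when courses are timed at mid-cycle and may cancel if products are compared on within-cycle change. PERMANOVA and the differential abundance tests were not simulated.

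The conclusion rests on one order for all women and on an assumed treatment rate. The gap is worth closing because the remedy is cheap and treatment dates are hard to recover afterwards.

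**What to change.** 1. Extend the on-study line in the Participants list: no antibiotics or antimycotics unless medically needed.
2. At each collection, record the start, stop and reason of any such course, unless the kit manual or timeline figure already provides for this.
3. Keep all samples in the main analysis, because a course may follow a reaction to a product.
4. Add a sensitivity analysis of the product contrasts (PERMANOVA, mixed effect model, differential abundance) without samples taken from the start of a course until 3 months after its end. Compare effect estimates and intervals, not significance alone: a result that loses significance in a smaller data set is not evidence of no product effect.
5. Report separately the courses that followed a product reaction. The simulation assigned courses independently of product and outcome, so it does not show that exclusion is unbiased in that case; leaving such samples out could selectively remove reactive women from the later products.
6. Varying the product order across women would remove the directional bias.

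Items 1 to 5 cost one protocol line, one short entry per collection (3 × 5 = 15 per woman), staff time to review the entries, and a repeat of tests already planned. They need no extra samples or visits. The sensitivity analysis would use about 2% to 9% fewer product cycles under the assumed rates. Varying the order needs a schedule for handing out the products in different sequences.

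### The protocol says product order need not vary; with one common order, product cannot be separated from cycle number or carry-over

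*Protocol*

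**What the plan says.** The Participants section sets out the exposure: "n = 100 for 5 menstrual cycles use each cycle another menstrual hygiene product". The five products, listed under Sample collection, are a tampon, a pad, a cup and two kinds of menstrual underwear. The same section adds: "Participants will have 3 sample collections for each menstrual product".

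Under Sample size calculation the protocol relies on comparisons within women: "we can perform paired analyses that allow us to account for intra-personal variation and increase power". It then states that "no wash-out period will be necessary during the different interventions, as this is already natural between 2 menstruations", and continues that "this also makes each participant a separate control and does not require varying the order of menstrual products".

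The readable text mentions no randomised or counterbalanced order, no sequence groups and no product-free comparison cycle. The split into 50 and 50 is by hormonal status, not by order of products. On analysis, the protocol says: "A PERMANOVA test will allow us to examine the overall effect of the intervention on the composition of the microbiome". A mixed model for alpha diversity, differential abundance tests and tests of taxa modules follow. No cycle or carry-over term is mentioned for any of them.

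**The concern.** The protocol draws a conclusion that its premise does not support. Self-control cancels whatever is constant within a woman. It does not cancel what changes between her first and fifth cycle, such as sampling practice, habituation and changes in behaviour. Depending on how the study is run, season, laboratory batch and the age of stored samples can change with cycle too. The interval between menstruations could at most limit carry-over. It does nothing about differences between cycles.

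With one common order, the k-th product is always used in cycle k and, from cycle 2 on, always follows the same product. Product, cycle and residual effect of the previous product then cannot be told apart. The claim that the interval is a sufficient wash-out also becomes untestable, because each product in cycles 2 to 5 has only one predecessor.

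The central aim is at stake: the influence of the product on the microbiome, metabolites and immune markers. Requiring several differential abundance tools to agree offers no protection, since all of them see the same confounded contrast.

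**Working it through.** The protocol gives no formal power calculation, so there is no figure of its own to reproduce. The question is first whether the product effect can be estimated, and then how large an error could be.

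**Inputs from the protocol.** 100 women, 5 cycles, one product per cycle (Participants); 5 products (Sample collection); order not required to vary (Sample size calculation).

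**Assumed, because the protocol gives no values.** One continuous outcome with one value per cycle, total SD 1, correlation ρ within women of 0.5 or 0.7, a linear drift of d SD per cycle, no true product effect, two-sided 5% tests.

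**Step 1: estimability.** The model is outcome = participant + product + cycle (+ first-order carry-over), with 100 × 5 = 500 rows. The rank of the design matrix is:

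| Terms | One common order | 10-sequence Williams design |
|---|---|---|
| participant + product | 104 | 104 |
| participant + cycle | 104 | 104 |
| participant + product + cycle | 104 | 108 |
| participant + product + cycle + carry-over | 104 | 112 |

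- One order: degrees of freedom for product after participant and cycle = 104 − 104 = 0.
- Williams design: 108 − 104 = 4. After carry-over is also included (rank without product 108): 112 − 108 = 4.

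Leaving out participants, product and cycle indicators together have rank 5 under one order; separating them needs 9. This result depends on no assumed drift, SD or correlation.

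**Step 2: size of the error under one order (illustrative).**

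First versus last product: the spurious difference is 4d, with standard error √(2(1−ρ)/100).
- ρ = 0.5, d = 0.05: z = 0.20/√(2×0.5/100) = 0.20/0.10 = 2.0, significant 52% of the time.
- ρ = 0.5, d = 0.10: z = 0.40/0.10 = 4.0, 98%.
- ρ = 0.7, d = 0.05: z = 0.20/√(2×0.3/100) = 0.20/0.0775 = 2.58, 73%.

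Omnibus test of five products: noncentral F with 4 and 396 degrees of freedom and noncentrality 100·Σ(dev²)/(1−ρ), where dev is the deviation of each cycle's drift from the mean drift, so that Σ(dev²) = 10d².
- ρ = 0.5, d = 0.05: 100×0.025/0.5 = 5, 39%.
- ρ = 0.5, d = 0.10: 100×0.10/0.5 = 20, 96%.
- ρ = 0.7, d = 0.05: 100×0.025/0.3 = 8.3, 62%.

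Milder cases at ρ = 0.5:
- Adjacent cycles, d = 0.05: z = 0.05/0.10 = 0.5, 7.9%.
- First versus last, d = 0.02: z = 0.08/0.10 = 0.8, 12.6% (omnibus 9.3%).
- First versus last, d = 0.01: z = 0.04/0.10 = 0.4, 6.9% (omnibus 6.0%).

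With drift expressed in within-person SD instead, a paired t-test of first versus last gives 29% at 0.05 and 80% at 0.10 per cycle with 100 women, and 17% and 50% with 50 women (one hormonal group). The two sets differ only in the unit of drift and in using t rather than z.

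**Step 3: what balancing costs in precision.** With 10 sequences of 10 women and σ² the within-person variance, a pairwise product contrast has variance 0.0200σ² after adjusting for cycle. That equals a simple paired comparison, 2/100 = 0.0200. With carry-over terms it is 0.0211σ², and 0.0211/0.0200 = 1.056, about 6% more. In this design each of the 20 ordered pairs of products occurs twice across the 10 sequences (10 × 4 = 40 transitions), and each product occurs twice in each cycle position.

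**The case against.** The strongest objection is that a common order is not documented. The protocol says the order need not vary, not that all women follow the same one, and the timeline figure is not available. If orders differ in practice, confounding is partial and a cycle term can be estimated. This stands: the statement that no analysis can repair the design is conditional on one common order. It does not rescue the stated rationale, and the readable text describes no allocation of orders.

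Second, the illustration uses one value per cycle, whereas three collections per product are planned. If one of them precedes menstruation, a change within the cycle could remove slow drift. This is fair, but the readable text gives neither the collection times nor such an analysis, and product would still be aliased with any change specific to a cycle.

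Third, first versus last under steady drift is the most biased of the ten pairs, and drifts of 0.01 to 0.02 SD do little harm. The calculation also does not carry over directly to PERMANOVA or to the rule that several tools must agree. The percentages are therefore illustrations, not estimates for this study.

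Fourth, some listed influences and analyses fall outside the aliasing. Laboratory batch is tied to cycle only if samples are processed by cycle. Staggered starts would loosen the link with season, though not with cycle number. The product before cycle 1 is the woman's habitual one and may vary. Under Techniques, metabolomics and ELISA on menstrual blood use the cup only, so they offer no comparison between products. Comparisons of pill with natural cycle within the same cycle are unaffected.

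These points narrow the consequences. None of them makes self-control a substitute for varying the order.

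**Conclusion.** The concern holds. The protocol's reason for not varying the order is invalid, and as written it permits a design in which the main product comparison cannot be attributed to the product. Under one common order, product keeps 0 of 4 degrees of freedom after cycle, against 4 of 4 under a balanced order; this is exact and needs no assumed effect size. The practical size of the bias is unknown. Under the assumptions shown, the false-positive rate for first versus last product at ρ = 0.5 runs from 6.9% at a drift of 0.01 SD per cycle to 98% at 0.10 SD. Because an analysis plan cannot recover a contrast that the design does not identify, this must be settled in the protocol, before participants start.

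**What to change.** Delete the statement that the order need not be varied, and state how the order is assigned. Randomise each woman to one of the 10 sequences of a Williams design for five products, stratified by combination pill and natural cycle: 100/10 = 10 women per sequence, 5 in each stratum. Each product then appears equally often in each cycle and follows every other product equally often, so the expected bias from cycle effects in product comparisons is zero. Include cycle number as a fixed effect in the product analyses and first-order carry-over as a sensitivity term; the model detail may sit in the analysis plan.

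If women have already gone through the products in one order, say so and word the conclusions as differences between product-cycle combinations.

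The cost is a randomisation list, kits packed in participant-specific order and slightly more complex distribution. No extra participants, visits, samples or assays are needed. Precision is unchanged after adjusting for cycle, and the variance rises by about 6% only where carry-over is also fitted.

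### Does naming only a PERMANOVA for overall composition commit the trial to an unpaired test on repeated samples?

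*Protocol*

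**What the plan says.** The design is within-person: "n = 100 for 5 menstrual cycles use each cycle another menstrual hygiene product". Under Sample collection, "Participants will have 3 sample collections for each menstrual product". Participants are split equally by contraception, 50 on the combination pill and 50 with a natural cycle.

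The section Sample size calculation gives no power calculation, on the ground that "the magnitude and variance of effects on the microbiome are unknown and are highly individual-dependent". It relies on the repeated-measures structure: "we can perform paired analyses that allow us to account for intra-personal variation and increase power". Under the same heading it then lists the analyses:

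- overall composition: "A PERMANOVA test will allow us to examine the overall effect of the intervention on the composition of the microbiome"
- alpha diversity: "This can be examined with a mixed effect model"
- differential abundance: "Three tools are capable of including random effects for paired analysis"
- for the vaginal microbiome, an effect on taxa modules.

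Of the first three, only the PERMANOVA has no device for the participant named beside it. The protocol states no permutation scheme, blocking factor or distance.

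**The concern.** A PERMANOVA in its simplest form shuffles labels over all samples, which is valid only if the samples are exchangeable. Repeated samples from one woman are not. The mixed model and the random effects are attached to the other methods only, so the text can be read as planning an unpaired test for the main question.

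Two consequences would follow:

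- **Product (within person).** Differences between women would stay in the permutation distribution, and the promised gain from pairing would be lost for this test.
- **Pill versus natural cycle (between persons).** Repeated samples would count as independent, and a true null would be rejected far too often.

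Both are real properties of free permutation. The question is whether the protocol commits the trial to it, and whether the damage would be as large as a near-total loss of power.

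**Working it through.** **Inputs.** From the protocol: 100 participants, 5 products, 3 collections per product, 50/50 by contraception. That gives 5 × 3 = 15 samples per participant and 100 × 15 = 1,500 per swab site. The protocol gives no effect size, variance, level or power, so there is no planned figure to reproduce. Assumed: level 5%, D independent Gaussian features with unit variance, Euclidean distance, and one product shifted. A share ρ of the variance lies between persons, and a share c is common to the collections of one cycle.

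**Product test under free permutation.** The reference distribution is approximately χ² with 4D degrees of freedom. With m collections per product, the actual statistic is f times a noncentral χ² with 4D degrees of freedom, where

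- f = 1 − ρ + (m − 1)c
- noncentrality = λ/f, with λ = 100 × m × δ² × (1 − 1/5)
- δ² is the sum of the squared shifts over features.

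**Power, c = 0.** Take a 0.3 SD shift in 3 of 15 features: δ² = 3 × 0.09 = 0.27. The critical value of χ² with 60 degrees of freedom is 79.08, so the free test rejects when the noncentral χ² exceeds 79.08/f.

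| m | λ | ρ | 79.08/f | λ/f | power, free | power, within participant |
|---|---|---|---|---|---|---|
| 1 | 21.6 | 0.3 | 113.0 | 30.9 | 8% | 77% |
| 1 | 21.6 | 0.5 | 158.2 | 43.2 | 0.2% | 93% |
| 3 | 64.8 | 0.3 | 113.0 | 92.6 | 97% | >99% |
| 3 | 64.8 | 0.5 | 158.2 | 129.6 | 90% | >99% |
| 3 | 64.8 | 0.7 | 263.6 | 216.0 | 64% | >99% |

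Simulations of the same setting agree. With one sample per product, free versus within-participant power was 7% versus 72–75% at ρ = 0.3 and 0–0.3% versus 91–95% at ρ = 0.5. With three collections, free power was 95–97% and 84–87%. The near-zero figures therefore come from one sample per product, not from the protocol's three.

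The loss still depends on the size of the shift. At 0.2 SD with three collections, free power was 22%, 0% and 0% at ρ = 0.3, 0.5 and 0.7, against 96–100% with restricted permutation.

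**Level when collections of a cycle resemble each other, m = 3.** Now f = 1 − ρ + 2c. The free test is conservative when 2c < ρ and anticonservative when 2c > ρ:

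- ρ = 0.3, c = 0: f = 0.7; rejection of a true null is below 0.01%.
- ρ = 0.3, c = 0.2: f = 1.1; 79.08/1.1 = 71.9; rejection 14% (simulated 15%).
- ρ = 0.2, c = 0.3: f = 1.4; 79.08/1.4 = 56.5; rejection 60%.
- ρ = 0.1, c = 0.3: f = 1.5; 79.08/1.5 = 52.7; rejection 74%.

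For the last two settings, simulation gave 55–69% under free permutation. It gave 2–3% when the three collections of a cycle were moved together within the participant.

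**Pill versus natural under free permutation.** The statistic is inflated by 1 + (k − 1)ρ for k samples per participant. At ρ = 0.3 and k = 5 the factor is 1 + 4 × 0.3 = 2.2, which gives a type I error of 60% with 10 features and 19% with one. At k = 15 the factor is 1 + 14 × 0.3 = 5.2, which gives 97% and 39%. The direction is not in doubt, but the protocol's PERMANOVA sentence concerns the intervention, that is, the products.

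**The case for a change.** The strongest case for a change is that the sample size rests on judgement and on pairing, so the overall test must deliver that pairing. The text names a participant device for two other methods and none for this one. Free permutation could err in either direction, depending on variances nobody knows, and the result could then not be interpreted. One or two sentences would settle the matter at no cost in data or participants. A comparison of contraceptive groups is also foreseeable in a sample split 50/50 on that factor.

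The statistical part of this stands: a freely permuted test would be miscalibrated. What does not follow is that the protocol plans one. A PERMANOVA with restricted permutation is still a PERMANOVA, and restriction is an ordinary option in standard software. The sentence promising paired analyses stands under the same heading as the list of tests and is naturally read as governing it. Silence beside one method is brevity, not a statement that this method is unpaired.

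Pairing alone does not settle one detail. If c > 0, shuffling single samples within a participant would still be wrong, and the three collections of a cycle must move together. That follows from the design, because the product is assigned to a cycle and not to a sample. It is the kind of choice an analysis plan records.

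**Conclusion.** The concern does not hold as a fault in the protocol. The permutation unit of the PERMANOVA is unstated, the stated principle of paired analysis points to the right kind of scheme, and such detail is commonly left to an analysis plan. Permutation within participant, with a cycle's collections kept together and each sample type analysed separately, holds the level within simulation error and has more than 99% power in the three-collection settings tabulated above. If contraceptive groups are compared, whole participants are the unit.

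The alarming figures are conditional on a scheme the protocol does not describe. The near-zero power also requires one sample per product in place of three, or a smaller shift. The type I error for pill versus natural cycle belongs to an unnamed test.

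All sizes rest on assumed correlations, shifts, feature counts, Euclidean distance and a 5% level. Restricted permutation does not separate product from cycle if every participant uses the products in the same order, which the protocol allows. That is a separate question of design and is not decided here.
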